Risk-benefit determination	
Neither UMA nor PMA are experimental procedures, thus the risk from the procedures itself is considered minimal. Surgeons at our institution have experience with both procedures in humans, albeit with more extensive experience with undersizing mitral annuloplasty and recent preliminary experience with papillary muscle approximation.
 
Proposed pre-operative and post-operative echocardiography and MRI are non-invasive, and thus the risk from these procedures is minimal as well. The data obtained from such imaging may not directly impact the patients care, however if any recurrence of FMR or deterioration in cardiac function is observed from the study imaging, the investigative team will inform the patient to consult their cardiologist. Thus, the patients stand to gain some benefit from participating in the study.
 
Overall, our study team determined that benefits significantly outweigh the risks to the patients participating in this study.

Number of sites enrolling participants	Emory University Hospital/Emory University Midtown Hospital/Emory St. Joseph's Hospital.
Study duration	20 years.
Participant duration	1 year from the time of surgery.

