## 2.0 OBJECTIVE

The primary objective of this protocol is to investigate if pre-operative inter-papillary muscle separation (IPMS) is predictive of FMR severity at 12 months after undersizing mitral annuloplasty (UMA) to repair functional mitral regurgitation (FMR). Furthermore, whether a cut-off value of pre-operative inter-papillary muscle separation can be established to predict patients who might have failure of UMA.

The secondary objective of this protocol is to investigate if adding papillary muscle approximation (PMA) to UMA is an effective technique in reducing recurrence of FMR at 12 months' post-procedure.

The third objective is to use computational modeling to define the impact that IPMS has on chordal force imbalance, to define the mechanistic basis for repair failure. MRI and echo images from the patients will be used to accomplish this objective.

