of FMR after annuloplasty. Since high or low are subjective terms, we seek to recruit 125 patients undergoing undersizing mitral annuloplasty (UMA) at our institution and measure their inter-papillary muscle separation before and after the procedure, and study their impact on 12 month outcomes of the repair. We will perform statistical analysis to determine a cut-off value for IPMS that can stratify patients at risk for UMA failure.

Using the patient specific imaging that we obtain from the 125 patients, we will perform comprehensive biomechanical computational modeling to demonstrate and validate that patients below the cut-off value of IPMS have better mitral valve force distribution, vs. those above the cut-off value of IPMS having poor mitral valve force distribution. This data will help validate the cut-off value as a viable technique to stratify patients for UMA.

In the final step of this study, we will demonstrate that those patients with higher IPMS and at risk of UMA failure, may benefit from a concomitant papillary muscle approximation technique. We will recruit 15 patients to a pilot study, in whom IPMS is above the cut off value, and perform papillary muscle approximation (PMS) along with undersizing mitral annuloplasty (UMA). We will investigate the effect of this combination approach on the outcomes at 6 months and 12 months.

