**Registry # 3: Retrospectively identified patients, who already underwent the standard of care surgery, and were identified after the procedure is completed, and are suitable for recruitment to the study for their post-operative research.**

**Rationale:** Historical review of patients between dates 1/1/2004 to present who have undergone mitral valve surgery who were not previously identified in the study. These patients have not been consented prior to their surgery. The purpose is to increase the study sample size in order to gain statistical power for outcome analysis.

Medical charts will be screened for patients who underwent surgery between 1/1/2004 to present for the lesion of interest at Emory, who would otherwise be eligible for this study but were not recruited as it was not known if they will need mitral valve surgery or were not recruited as they may have received the surgery prior to study start date.

Study assignment: 140 patients will be recruited in total, 1) n=125 to undersizing mitral annuloplasty (UMA) and 2) n=15 to undersizing mitral annuloplasty with papillary muscle approximation (UMA+PMA). Selection will be in a non-randomized manner. Under no circumstances will more than the proposed number of patients be recruited to either groups, without prior approval from the institutional IRB and the study sponsor.

Surgical procedures:

[figure not shown]
Intra-operative echo 1: On the day of the surgery, after the patients are sedated, intubated and anesthetized, the cardiac anesthesiologist will perform a standard of care transesophageal echocardiogram.

Surgical procedures:

*Undersizing mitral annuloplasty (Figure A):* Patients undergoing this procedure will receive a commercially available annuloplasty ring of the surgeon's choice. Sutures are placed around the mitral annulus, and the metallic ring is then implanted onto the mitral annulus to reduce it in size.

*Undersizing mitral annuloplasty with papillary muscle approximation (Figure B):* Patients receiving this procedure will undergo undersizing mitral annuloplasty in a manner that is identical to the procedure outlined above. In addition to the ring implantation, one or two 4-0 pledgedet suture are used to draw the two papillary muscle tips together to reduce the IPMS.

After the procedure is complete, the patients are revived from cardiopulmonary bypass and hemodynamic stability is established.

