## **12.0 ADVERSE EVENT REPORTING**

**Considering the observational nature of this study, and lack of any experimental procedures, adverse event reporting will be limited only to those events that may occur from the specific non-standard of care lab procedures that are performed at 6 and 12 month visits. Adverse events at these 6 and 12 month visits are described here.**

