### 11.1 Definitions

**Adverse events:** An adverse event is any undesirable clinical occurrence in a study patient, that is related to a study intervention that is non-standard of care. Any condition that was recorded as pre-existing or that is associated with standard of care procedures that the patient has consented to is not an AE unless there is a change in the nature, severity or degree of the condition.

**Serious Adverse Events (SAE):** Serious adverse events are defined by FDA regulation as any experience that results in a fatality or is life threatening; results in significant or persistent disability; requires or prolongs a hospitalization; or represents other significant hazards or potentially serious harm to research subjects or others, in the opinion of the investigators. Important medical events that may not result in death, be life-threatening, or require hospitalization may be considered a serious adverse event when, based upon appropriate medical judgment, they may jeopardize the patient and may require medical or surgical

intervention to prevent one of the outcomes listed in this definition. Examples of such medical events include bronchospasm requiring intensive treatment in an emergency room or at home, blood dyscrasias, or convulsions that do not result in inpatient hospitalization.

*Unanticipated Serious Adverse Event:* An unanticipated (unexpected) serious adverse event is any serious adverse event that is not protocol-defined or documented in the patient consent form. Expedited reporting is required for serious adverse events that are unexpected.

*Event Recording:* The following adverse events will be captured throughout the period of trial participation:

- Protocol-defined (as described below)
- Serious unanticipated events (serious “Other” adverse events)

*Causality:* The investigator will assess the relationship of an adverse event to the proposed non-standard of care lab assessments and imaging studies. Causality will be defined as follows:

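### Papillary muscle approximation (PMA) is assigned by protocol to 15 patients but treated as non-experimental, and the safety sections conflict on recording surgical events and never attribute them to PMA

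*Combined protocol and SAP*

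**What the plan says.** **Assignment and purpose.** Section 3.0 (Background) states: "We will recruit 15 patients to a pilot study, in whom IPMS is above the cut off value, and perform papillary muscle approximation" together with UMA. The threshold of inter-papillary muscle separation (IPMS) comes from this study: "We will perform statistical analysis to determine a cut-off value for IPMS that can stratify patients at risk for UMA failure". Section 7.2, under *Study assignment*, fixes 125 patients for UMA and 15 for UMA+PMA and adds: "Selection will be in a non-randomized manner". Section 2.0 makes it the secondary objective to "investigate if adding papillary muscle approximation (PMA) to UMA is an effective technique in reducing recurrence of FMR at 12 months' post-procedure".

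**Risk.** The risk-benefit row of section 1.0 says: "Neither UMA nor PMA are experimental procedures, thus the risk from the procedures itself is considered minimal". It then describes the local surgeons as having more extensive experience with UMA and "recent preliminary experience with papillary muscle approximation". Section 3.0 calls UMA the current standard of care; no section says so of PMA by name.

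**Safety reporting, narrow text.** Section 12.0 opens by citing the observational design and the "lack of any experimental procedures, adverse event reporting will be limited only to those events" arising from non-standard laboratory procedures at the 6- and 12-month visits. In the subsection numbered 11.1, the investigator judges causality only against non-standard laboratory and imaging studies.

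**Safety reporting, wide text.** The same subsection says that protocol-defined events are captured over the whole of each patient's participation. The *Specific Adverse Event Definitions* include peri-operative events. Section 10.0 (Monitoring) puts serious and protocol-defined adverse events among the data that are fully source-verified. *Reporting of Serious Adverse Events* requires protocol-defined serious events to be reported.

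**The concern.** Calling a procedure non-experimental is a label and says nothing about how often it does harm. The inference from that label to minimal risk also sits badly with the admission of only preliminary local experience, and with a protocol that selects patients for the procedure in order to learn whether it works.

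The label has consequences because section 12.0 gives the absence of experimental procedures as a reason for narrowing adverse event reporting. The pilot is intended to show that patients with high IPMS may benefit from PMA. If complications of the added step are recorded inconsistently, or recorded without any judgement of their relation to PMA, the regurgitation result would be presented without the harm that belongs beside it.

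**Working it through.** **1. Group sizes.** Sections 1.0 and 7.2 give 125 + 15 = 140. Section 11.0 gives 50 in phase 1 and 75 + 15 = 90 in phase 2, so 50 + 90 = 140 and 50 + 75 = 125 for UMA. The figures agree. Section 11.0 says that the PMA arm is a pilot not based on a power analysis, so there is no power calculation to test. The rest is a comparison of text.

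**2. Is PMA a study procedure for these patients?** Section 3.0 selects them by a study-derived threshold and performs PMA. Section 7.2 lists UMA+PMA as an assignment of fixed size that may not be exceeded without IRB and sponsor approval. Section 2.0 tests its effectiveness. The threshold rule is explicit only in section 3.0; section 7.2 says only that selection is non-randomized. Together these make PMA a protocol-assigned procedure whose effect is under study.

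**3. Two readings of the safety text.**

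| Text followed | Surgical complication recorded as an adverse event? | Relation to PMA assessed? |
|---|---|---|
| Opening of section 12.0 (6- and 12-month laboratory procedures only) | No | No |
| Event recording in 11.1, the specific definitions and section 10.0 | Yes | No: causality refers only to laboratory and imaging studies |

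The readings differ on recording. They agree that no rule attributes an event to PMA. The *Probable* category refers to follow-up imaging and blood draws. *Possible* and *Unlikely* refer to a non-standard procedure, which the lead-in to the causality rules limits to laboratory and imaging studies.

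**4. What the endpoints already cover.** The secondary endpoints in sections 1.0 and 9.0 collect death, stroke, worsening heart failure, heart failure hospitalization, mitral re-intervention and readmission. Bleeding, infarction, arrhythmia, renal events and infection are not endpoints. A readmission endpoint cannot pick them up when they occur during the index hospital stay.

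**5. One route that depends on the label.** Deaths related to participation and associated with non-standard procedures go promptly to the IRB; unrelated deaths go at continuing review. The text does not settle which route a death after PMA would take.

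**6. What 15 patients can show.** With 0 events in 15, the one-sided 95% upper limit is 1 − 0.05^(1/15) = 0.181, and the upper end of the two-sided 95% interval is 1 − 0.025^(1/15) = 0.218. The documents give no PMA complication rate. For assumed true rates of 2%, 5%, 10% and 20%, the chance of at least one event, 1 − (1 − p)^15, is 26%, 54%, 79% and 96%. These figures are context only: they argue for descriptive reporting and do not measure the defect.

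**The case against.** The strongest reply is that the protocol does intend to record surgical events. The definitions include heavy transfusion in the first 24 hours after surgery, re-operation for hemorrhage, ventilation beyond 48 hours and wound dehiscence. A blood draw or scan at 6 or 12 months cannot plausibly cause these, so the list has little purpose unless surgical events are captured. Section 10.0 source-verifies them, and the serious-event duty carries no causality condition in the sentence that creates it. The definition in 11.1 covers an event "that is related to a study intervention that is non-standard of care"; since no section names PMA as standard of care, that wording could include PMA.

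This stands, and it rules out two stronger readings. A reader might infer that PMA complications are plainly not counted as adverse events, or that serious ones would never reach the reporting route. The documents support neither: they contradict themselves on recording, and they require protocol-defined serious events to be reported. A reader might also infer from the titles of the two cited PMA papers, which refer to severe ischemic disease, that the evidence does not fit the wider population admitted here. Titles alone cannot carry that.

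It is also fair that a 15-patient pilot could not establish low risk under any reporting scheme, and that section 1.0 does not claim that it will. None of this supplies a rule for attributing an event to PMA, or removes the conflict with the opening of section 12.0.

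**Conclusion.** The point holds as an internal contradiction with a gap that remains under either reading. PMA is assigned by the protocol and its effectiveness is tested, yet its risk is called minimal because it is said not to be experimental. That premise then supports a restriction on adverse event reporting which conflicts with the event list, the source-verification rule and the serious-event rule. No reading provides for assessing relation to PMA.

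The gap concerns all 15 patients of the PMA group, 15/140 = 10.7% of planned enrolment. How many events would be missed or left unattributed cannot be derived from the documents. The conclusion rests on reading the causality lead-in as limiting the categories under it, and on taking sections 2.0, 3.0 and 7.2 together as assigning PMA. It should be corrected, because the pilot's account of benefit is incomplete without attributable harm.

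**What to change.** Reconcile the risk-benefit row of section 1.0, section 3.0 and section 12.0 with its subsections:

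- In section 1.0, delete the inference from non-experimental to minimal risk as it applies to PMA.
- In the opening of section 12.0, replace the restriction to 6- and 12-month laboratory procedures. Record the events already defined there from surgery to 12 months in prospectively enrolled patients of both groups. Events in the UMA+PMA group alone could not be separated from those of annuloplasty or concomitant surgery.
- In the causality rules, add relation to PMA for Group 2.
- Report serious events through the existing serious-event route.
- Tabulate events by group beside the mitral regurgitation results, descriptively, given n = 15 and non-randomized groups.

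Whether the pilot should be relabelled interventional is for the sponsor and the IRB to decide.

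The cost is a protocol amendment, extra chart abstraction and reporting in both groups using existing definitions, and a less favourable risk statement. No treatment changes.

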## 2.0 OBJECTIVE

The primary objective of this protocol is to investigate if pre-operative inter-papillary muscle separation (IPMS) is predictive of FMR severity at 12 months after undersizing mitral annuloplasty (UMA) to repair functional mitral regurgitation (FMR). Furthermore, whether a cut-off value of pre-operative inter-papillary muscle separation can be established to predict patients who might have failure of UMA.

The secondary objective of this protocol is to investigate if adding papillary muscle approximation (PMA) to UMA is an effective technique in reducing recurrence of FMR at 12 months' post-procedure.

The third objective is to use computational modeling to define the impact that IPMS has on chordal force imbalance, to define the mechanistic basis for repair failure. MRI and echo images from the patients will be used to accomplish this objective.

### **3.0 BACKGROUND**

Functional mitral regurgitation (FMR) is a frequently diagnosed mitral valve lesion in patients surviving cardiomyopathies of ischemic and non-ischemic origins. Volume overload from FMR increases the risk of congestive heart failure and death. Pharmacological management of these patients has been shown to be ineffective, and thus timely repair of FMR is considered to benefit the patient and preserve their cardiac function.

Undersizing mitral annuloplasty (UMA) is the current standard of care to repair FMR, which involves placing a metallic ring onto the mitral annulus, to reduce its dimensions. This procedure can be performed using open heart surgical techniques or with transcatheter mitral valve techniques. Though UMA is considered effective, there is increasing evidence that FMR persists or recurs after the procedure. At 12 months, ~36% of the patients present with recurrence FMR, which increases to 58% at 24 months. The mechanisms driving failure of UMA are unknown, and a metric for pre-operative stratification of patients to benefit from UMA is necessary.

Our group recently reported that in patients presenting with FMR, inter-papillary muscle separation (IPMS) has a strong correlation with the pre-operative severity of the regurgitation. Using cardiac MRI imaging, we demonstrated that IPMS directly impacted the extent of leaflet tethering and mitral regurgitation, independent of the left ventricular size or volume. We used biomechanical modeling to demonstrate that elevated IPMS increases the forces in the marginal chordae, resulting in improper leaflet closure.

In a more recent study in a bench-top ex-vivo model, we demonstrated that IPMS can also have an impact on mitral valve closure after undersizing mitral annuloplasty (UMA). Specifically, we demonstrate that when the IPMS is elevated, UMA results in a highly unphysiological leaflet geometry that results in persistent FMR despite the repair. In a similar study in swine, we demonstrated that such an unphysiological leaflet configuration after UMA can be improved with papillary muscle approximation (PMA).

In this observational, prospective, non-randomized clinical study, we seek to test the hypothesis that elevated pre-operative inter-papillary muscle separation (IPMS) is a risk factor for recurrence

of FMR after annuloplasty. Since high or low are subjective terms, we seek to recruit 125 patients undergoing undersizing mitral annuloplasty (UMA) at our institution and measure their inter-papillary muscle separation before and after the procedure, and study their impact on 12 month outcomes of the repair. We will perform statistical analysis to determine a cut-off value for IPMS that can stratify patients at risk for UMA failure.

Using the patient specific imaging that we obtain from the 125 patients, we will perform comprehensive biomechanical computational modeling to demonstrate and validate that patients below the cut-off value of IPMS have better mitral valve force distribution, vs. those above the cut-off value of IPMS having poor mitral valve force distribution. This data will help validate the cut-off value as a viable technique to stratify patients for UMA.

In the final step of this study, we will demonstrate that those patients with higher IPMS and at risk of UMA failure, may benefit from a concomitant papillary muscle approximation technique. We will recruit 15 patients to a pilot study, in whom IPMS is above the cut off value, and perform papillary muscle approximation (PMS) along with undersizing mitral annuloplasty (UMA). We will investigate the effect of this combination approach on the outcomes at 6 months and 12 months.

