Post-chest closure echo: Just prior to moving the patient out of the operating room, a repeat intra-operative standard-of-care echocardiogram will be performed to assess the valve function. After both procedures, the patients are revived from surgery and their post-operative care will follow established and standard of care protocols.

Follow-up time points and examinations:

*Discharge:* Following examinations will be performed before discharge:

- Transthoracic echocardiography

- Blood draw

*30-day (+/- 7 days):* Following examinations will be performed at 30-days :

- Blood draw
- Transthoracic echocardiography

*6 months post-surgery (+/- 30 days):* Following examinations will be performed at discharge at 6 months post-surgery

- Transthoracic echocardiography
- Blood draw
- Quality of life questionnaire
- HF questionnaire
- 6 minute walk test

*12 months post-surgery (+/- 90 days):* Following examinations will be performed at discharge at 6 months post-surgery

- Transthoracic echocardiography
- Cardiac MRI with contrast or transesophageal echo (whichever is possible)
- Blood draw
- QoL questionnaire
- Heart failure questionnaire
- 6MWT

Computational biomechanical modeling: Echocardiographic images, immediately after acquisition will be transferred to the core database established by the PI's laboratory. These images obtained from the patients at the different timepoints will be used for computational biomechanical modeling. The 3D echocardiographic images will be segmented and a mathematical mesh will be developed. Idealized material properties will be assigned to the mesh geometry, and the strain and stress distribution on the leaflets will be quantified under different loading conditions.

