## 11.0 ANALYSIS PLAN

**General design issues:** This is an observational, prospective, non-randomized, single center, multiple phase study. Enrolled patients will have clinically significant FMR with either ischemic or non-ischemic cardiomyopathies. 50 patients are recruited to phase 1 (all 50 receiving undersizing mitral annuloplasty), and 90 patients to phase 2 (75 receiving undersizing mitral annuloplasty and 15 receiving undersizing mitral annuloplasty and papillary muscle approximation). In patients

receiving undersizing mitral annuloplasty, the same rigid annuloplasty ring will be used as consistently as possible, and up to two sizes of downsizing will be performed as consistently as possible. In some patients recruited to the study, the surgeon may decide to switch to mitral valve replacement, or may perform a repair and deem it to be a failure and then switch to mitral valve replacement. In either case, the patient will continue to be part of the study, but with follow-up performed only at 12 months.

**Sample size estimation and statistical analysis plan:** The primary objective of this study is to determine the correlation between pre-operative inter-papillary muscle separation and the 6 month and 12 month post-operative FMR grade after undersizing mitral annuloplasty. Pre-operative inter-papillary muscle separation will be measured and is a continuous variable, while the recurrence of FMR will be deemed binary (1: if MR greater than or equal to 2+ severity observed at 12 months; 0: if MR less than or equal to 2+ severity observed at 12 months). An ROC curve analysis will be used to determine the inflection point of inter-papillary muscle separation at which FMR will recur at 12 months after annuloplasty. Sample sizes are based on previously published data, and on ensuring the ability to detect with high probability, a clinically meaningful presumed benefit for patients undergoing mitral valve repair.

Recruitment to the papillary muscle approximation arm is not based on power analysis as it is only a pilot study.

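### The comparison of modelled forces below and above the IPMS cut-off is offered as help in validating it, but shows only that IPMS relates to force, not that the cut-off predicts UMA failure

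*Combined protocol and SAP*

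**What the plan says.** The cut-off comes from section 11.0 (Analysis Plan), which relates pre-operative IPMS to recurrence coded as yes or no: "An ROC curve analysis will be used to determine the inflection point of inter-papillary muscle separation at which FMR will recur at 12 months".

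Section 3.0 (Background) then describes a modelling step in the patients who supply the cut-off: "Using the patient specific imaging that we obtain from the 125 patients". Its purpose is to "validate that patients below the cut-off value of IPMS have better mitral valve force distribution" than those above it. The inference drawn is: "This data will help validate the cut-off value as a viable technique to stratify patients for UMA".

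On what is already known, the same section says of patients presenting with FMR: "We used biomechanical modeling to demonstrate that elevated IPMS increases the forces in the marginal chordae". Section 2.0 (Objective) lists the modelling as a third, mechanistic objective. Section 7.2 (Overview of study design) describes the model itself: "Idealized material properties will be assigned to the mesh geometry, and the strain and stress distribution on the leaflets will be quantified under different loading".

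Section 11.0 describes no held-out sample, cross-validation, bootstrap or optimism correction for the cut-off, and does not mention the modelling step.

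**The concern.** In the below/above comparison, pre-operative IPMS defines the groups and modelled force is what is compared. The 12-month MR result is neither. If IPMS and modelled force are related, as the protocol says they are before repair, the groups will tend to differ in force wherever the line is drawn, whether or not that line has anything to do with recurrence.

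What is at stake is the claim the study may make. A cut-off picked by ROC in one sample is prone to optimism, and a validation step should be able to expose a spurious one. This step cannot, yet its result would be reported as support for using the cut-off to select patients for UMA. Within this study the cut-off also defines who is eligible for the 15-patient UMA+PMA pilot (section 3.0).

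**Working it through.** **1. The plan's own figures.** Section 11.0 gives 50 UMA patients in phase 1 and 75 in phase 2: 50 + 75 = 125. Adding the 15 UMA+PMA patients gives 140. Both totals agree with the rest of the protocol. The number 125 cannot be derived further, because no alpha, power, target AUC, correlation or dropout is stated.

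**2. The two steps side by side.**

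| Step | Groups defined by | Quantity compared | Uses 12-month recurrence? |
|---|---|---|---|
| ROC (11.0) | recurrence yes/no | pre-operative IPMS | yes |
| Force comparison (3.0) | IPMS below/above cut-off | modelled force distribution | no |

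The second step adds no information about recurrence to the first.

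**3. How often a worthless cut-off would pass.**
- From the documents: N = 125; 12-month recurrence 32.6% (section 1.0; section 3.0 gives about 36%).
- Assumed, because the documents are silent: IPMS x is standard normal; modelled force is f = r·x + √(1 − r²)·e, with e standard normal; recurrence is independent of both, so the true AUC is 0.50; a pass is a two-sided t-test at 0.05 with higher force above the cut-off.
- The cut-off is either fixed at a percentile of IPMS or set at the maximum of the Youden index J = sensitivity + specificity − 1.
- The fixed cut-offs were simulated with 1,500 trials per setting. A range in the last column spans two simulations, of 1,500 and 4,000 trials per setting.

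| r | Fixed cut-offs, 10th to 90th percentile | Youden cut-off chosen on noise |
|---|---|---|
| 0 | about 3% | 2-3% |
| 0.2 | 24-42% | 32% |
| 0.3 | 44-78% | 60-61% |
| 0.4 | 71-97% | 82-85% |
| 0.5 | 88-99.9% | 90-93% |
| 0.6 | 98-100% | 94% |
| 0.7 | 99.5-100% | 95-97% |

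The pass rate depends on r and on where the cut-off falls, not on any link between IPMS and recurrence, because there is none in these data.

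**4. Why the ROC step needs its own check.** In the same null data the Youden cut-off shows a mean apparent J of about 0.11 (true value 0). A naive Fisher test of that cut-off against recurrence gives p < 0.05 in about 16-18% of trials, against a nominal 5%.

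**5. What a recurrence-based check could deliver.** Suppose the cut-off is locked in phase 1 and tested in the 75 phase-2 UMA patients.
- Expected recurrences: 50 × 0.326 = 16.3 to 50 × 0.36 = 18 in phase 1; 75 × 0.326 = 24.4 to 75 × 0.36 = 27 in phase 2.
- Hanley-McNeil: SE² = [A(1 − A) + (n₁ − 1)(B − A²) + (n₀ − 1)(C − A²)]/(n₁n₀), with B = A/(2 − A) and C = 2A²/(1 + A).
- For A = 0.70, n₁ = 24, n₀ = 51: B = 0.5385, C = 0.5765. SE² = (0.21 + 23 × 0.0485 + 50 × 0.0865)/1,224 = 5.65/1,224 = 0.0046, so SE = 0.068. The 95% half-width is 1.96 × 0.068 = 0.133 (0.128 with 27 and 48).
- Power against AUC 0.50 (null SE 0.0719): Φ[(0.20 − 1.96 × 0.0719)/0.0679] = Φ(0.87) = 81% (83% with 27 and 48). At a true AUC of 0.65 it is 55-58%.
- At an assumed sensitivity and specificity of 0.75: sensitivity half-width 1.96√(0.75 × 0.25/24) = 0.173 (0.163 with 27); specificity half-width 1.96√(0.75 × 0.25/51) = 0.119 (0.122 with 48).
- With no true relation, the AUC test would pass about 2.5% of the time. Deaths and dropout before 12 months are not allowed for.

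**The case against.** The text is softer than a formal rule. It sits in the Background, says only that the data will help, and sets no test or threshold. Explaining mechanism is a legitimate aim in its own right (third objective, section 2.0). Recurrence does enter where the cut-off is derived, no decision in the protocol hangs on the modelling result, and the primary endpoint is untouched. All of this stands. It limits the point to the inference drawn from the force comparison; it does not rescue that inference.

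A reader might infer that almost any cut-off would pass. The documents do not support that. They give no IPMS-force correlation. At r of 0.3 or less many cut-offs would fail; the statement holds for r of about 0.5 or more, and for central cut-offs at 0.4. The prior modelling result concerns valves before repair. Section 1.0 plans forces before repair, after repair and at follow-up, and section 3.0 does not say which are compared. Post-repair forces may correlate less with IPMS, and follow-up images may carry some trace of the repair's outcome. The compared quantity is also unsettled: section 3.0 speaks of force distribution, section 2.0 of chordal force imbalance and section 7.2 of leaflet strain and stress.

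A reader might also think that comparing force between patients with and without recurrence would validate the cut-off. It would not: force could predict recurrence independently of IPMS while the IPMS cut-off was useless. That comparison tests the mechanism only.

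**Conclusion.** The point holds in a limited form. A better modelled force distribution below the cut-off than above it would show that IPMS relates to modelled force, which the protocol already reports for valves before repair. It would not show that the cut-off predicts UMA failure, and no other step validates the cut-off. This follows from the text and needs no simulation.

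The size is illustrative. Under the assumptions above, a cut-off with no predictive value passes in about one third of trials at r = 0.2 and in nine out of ten or more at r = 0.5 and above. The result rests on an assumed correlation, an assumed t-test criterion and a single linear force measure.

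It would go too far to say that the cut-off ignores recurrence, or that the protocol will declare it validated on modelling alone: section 11.0 derives it from recurrence, and section 3.0 claims only help. The plan should be changed because, as written, it supports a statement about patient selection that the analysis cannot carry.

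**What to change.** 1. In section 3.0, describe the below/above force comparison as mechanistic support under the third objective, and remove the statement that it helps to validate the cut-off. State which time point's forces, and which model output, are compared.
2. In section 11.0, add validation of the cut-off against 12-month recurrence in the UMA patients. Either repeat the whole ROC and cut-off selection in bootstrap samples and report optimism-corrected AUC, sensitivity and specificity, or lock the cut-off in the 50 phase-1 patients and test it in the 75 phase-2 UMA patients. If the second route is taken, note that the 15 UMA+PMA patients are drawn from above the cut-off, which may thin that range in the phase-2 UMA group.
3. First resolve the outcome coding in section 11.0, where MR of exactly 2+ falls into both the recurrence and the no-recurrence category.
4. As a mechanistic analysis only, report modelled force by 12-month recurrence status, adjusted for IPMS.

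The cost is protocol wording and analysis of data already planned for collection, with no new patients or procedures. The downside is that the force comparison can no longer be reported as validation, and that the corrected ROC performance will look slightly less favourable.
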